### 13 PROTOCOL STEERING COMMITTEE

The Protocol Steering Committee will ensure the study meets its objectives to identify a well-tolerated and optimally effective dose of moxidectin for scabies. The Committee will be comprised of up to two external experts, up to two Sponsor representatives not directly involved in management of the study, and a statistician.

The Committee will review relevant accumulated unblinded safety and efficacy data for all randomized subjects collected through to the review cutoff date. The data review cutoff date will correspond to the date when the first 3 subjects in each of the 3 initial treatment arms have completed their Day 14 study evaluation. Study recruitment may be paused during the review period.

Based on a review of the available data, the Committee will recommend one or more of the following actions:

- Continuation of the study with no dose modification to the target sample size of 6 subjects per cohort; or,
- Stopping recruitment of one or more of the current dose cohorts; and/or,
- The addition of a 36 mg dose cohort.

Should design modifications be recommended, the study will maintain the randomized allocation of subjects to the remaining/additional treatment cohorts, to a target sample size of 6 subjects.

The decision-making process of the Committee will be guided by:

- The mortality rate of adult scabies mites, or the time-to-death of adult scabies mites. Subject-level review may also be considered.
- Safety outcomes, such as the frequency, nature and severity of adverse events, and withdrawal rates.
- Pharmacokinetic data may be reviewed if available.

The Committee will not reveal the results of their data review or, barring any unanticipated safety issues, any decisions or recommendations to Investigators, study personnel, or Sponsor personnel involved in the management of day-to-day study activities ([Section 10.2](#)).

Minutes of the Protocol Steering Committee meetings as well as the interim data reviewed will be documented but remain confidential until the study's conclusion. Additional unblinded reviews and possible dose modification recommendations may also be undertaken by the Committee at any time at, or in lieu of the data review described above, at the request of the Sponsor.

Further details can be found in the Protocol Steering Committee Charter.

## **14 SUBJECT COMPLETION/WITHDRAWAL**

### **14.1 Subject Completion**

A subject will be deemed to have completed the study once all trial procedures have been conducted. Any AEs or SAEs still ongoing at the time of the Exit Evaluation will be followed in accordance with [Section 12](#).

### **14.2 Criteria for Premature Withdrawal from Treatment or the Study**

Subjects have the right to withdraw from the study at any time for any reason. The Investigator must make every reasonable effort to keep each subject in the study except where termination or withdrawal is for reasons of safety. The Investigator also has the right to withdraw patients from treatment or the study in the event of concurrent illness, AEs, pregnancy, treatment failure after a prescribed procedure, protocol violations, administrative reasons or other reasons. The reasons for withdrawal of the subject must be recorded on the CRF.

It is understood by all concerned that an excessive rate of withdrawals from the study can render the study difficult to interpret. Unnecessary withdrawal of subjects from the study should be avoided.

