## **12.9 Procedures to be Followed in the Event of Pregnancy**

The subject must be instructed to inform the Investigator **immediately** if she becomes pregnant during the study period or if his partner becomes pregnant. The Investigator should report all pregnancies to the Sponsor or designee within 24 hours of becoming aware of the pregnancy. Pregnancies should be reported using Clinical Pregnancy Notification Form provided by the Sponsor for reporting the occurrence and outcome of pregnancies in subject enrolled in the study.

The subject should be monitored until the end of the pregnancy and the outcome of the pregnancy should be reported to the Sponsor.

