### **14.3 Withdrawal of Subjects from Study Product**

Treatment withdrawal is not relevant in this single dose study.

If a subject is unable to swallow all required tablets and take the full dose of IMP, they should remain on-study and be followed up according to the protocol.

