### **14.5 Replacement of Withdrawn Subjects**

Any subjects who discontinues in a clinical study of their own volition or by the Investigator are defined as “withdrawals”. Replacement subjects may be enrolled into the study at the request of the Sponsor. They will receive the same treatment allocation as the withdrawn subject by use of a matching replacement subject number pre-assigned for each subject. This is to ensure that blinding is maintained. Further details are provided in the Study Reference Manual.

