#### **6.10.3.4 Clinical Cure Rate**

Clinical cure rate is defined as resolution of all scabies signs and symptoms present at Baseline, no new scabies signs and symptoms and no evidence of mites by dermoscopy.

Clinical cure rate will be assessed at Days 7, 14 and 28. At each of these visits, a subject will be considered a responder, as determined by the clinician reported scabies signs and symptoms, if region status is 'Region clear from previous assessment', for each anatomical region assessed at that visit.

For each subject, imputation of missing assessments will be applied as follows. Where the scabies signs and symptoms assessment has been completed for a visit but this includes a missing assessment for a region previously assessed at an earlier time point, the region status will be imputed using the most recent previous assessment for the respective region (last observation carried forward). However, if the scabies signs and symptoms assessment has not been completed for a visit, or the assessments for all regions previously assessed are missing, no imputation will be applied and the subject will be excluded from the denominator for clinical cure rate at that visit.

Where rescue medication has been taken (identified on the concomitant medications page of the eCRF), any assessment indicating clinical cure response subsequent to the start date of rescue medication will be ignored and the subject will be considered a non-responder. Visit responses identified at any visit prior to or on the start date of rescue medication for the subject will be unaffected.

The number and percentage of responders, together with the Clopper-Pearson 95% CI for the percentage, will be presented for each dose group at each post-Baseline visit. The denominator for all percentages will be the number of subjects with a non-missing scabies signs and symptoms assessment for the respective dose group and visit and this will also be presented in the summary.

A flag will be added to the listing of scabies signs and symptoms data to indicate subjects identified as responders at each time point.

Following review of the above summaries, additional post hoc analyses may be considered, for example sensitivity analyses repeating the above clinical cure rate summary without imputation for missing assessments or the use of rescue medication. Any post-hoc analyses to be performed will be fully defined in a SAP Addendum prior to conducting the analyses.

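### Protocol 14.2 lets the investigator end follow-up for outcome-related reasons after a single dose, and SAP 6.10.3.4 then drops a withdrawn failure from the Day 28 cure denominator

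*Protocol*

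**What the plan says.** **Permission.** Protocol 14.2 lets the investigator "withdraw patients from treatment or the study in the event of concurrent illness, AEs, pregnancy, treatment failure after a prescribed procedure, protocol violations", and for administrative or other reasons. The same section sets a retention duty, "The Investigator must make every reasonable effort to keep each subject in the study except where termination or withdrawal is for reasons of safety", and adds "Unnecessary withdrawal of subjects from the study should be avoided". Reasons for withdrawal go on the CRF.

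**Treatment.** Section 14.3 says "Treatment withdrawal is not relevant in this single dose study", and 12.6 says the same of dose modification and discontinuation. Section 14.3 also keeps a subject who could not take the full dose in follow-up.

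**Exit assessments.** Sections 9.3.6 and 14.4 are worded for a subject who chooses to leave. Before Day 28, 9.3.6 adds a PK sample, RCM, dermoscopy, clinical signs and patient-reported outcomes (PROs). The Table 1 footnote also covers subjects who are withdrawn, but lists only safety procedures. Section 14.5 counts investigator withdrawals as withdrawals and states "Replacement subjects may be enrolled into the study at the request of the Sponsor".

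**Other follow-up.** Section 11.2.3 allows rescue from Day 14 when mites are confirmed by RCM. On pregnancy, 12.9 says "The subject should be monitored until the end of the pregnancy". Sections 12.2.2 and 12.4 tie AE reporting and follow-up to the end of the study or to 28 and 30 days after dosing, whichever is later.

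**Analysis.** SAP 6.10.1.3 carries the last mite status forward after early withdrawal. For clinical cure, when the whole visit assessment is missing, SAP 6.10.3.4 says "no imputation will be applied and the subject will be excluded from the denominator for clinical cure rate at that visit". An apparent cure after the start of rescue is scored as non-response. SAP 6.4 maps exit data collected before Day 28 to a separate Early Withdrawal visit.

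**The concern.** All study drug is given on Day 0. Withdrawing a dosed subject from the study therefore removes no exposure and only ends scheduled observation. Several of the listed grounds (AEs, treatment failure) are themselves outcomes, so the missing data can depend on how the subject did.

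The trial has about 6 subjects per dose and its primary objectives are to choose a dose and to evaluate safety. One subject is about 17% of an arm. If failures can leave an efficacy denominator at the investigator's discretion, an arm's cure rate can rise without any more subjects being cured. Arms with more failures have more to gain, so differences between doses can be blurred.

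**Working it through.** The plan states no power, alpha-based sample size or dropout figure, so there is nothing of its own to reproduce. The only planning input is about 6 subjects per dose (Protocol 15.3). All cure counts, withdrawal counts and AE rates below are assumptions.

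**Step 1: what the permission can mean.** 14.2 offers withdrawal from treatment or from the study. 12.6 and 14.3 make the first empty after dosing, so only study withdrawal remains. No section says that a subject withdrawn by the investigator continues scheduled visits to Day 28 or Week 12.

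**Step 2: which exit assessments apply.** For an investigator withdrawal, the text that clearly applies is the Table 1 footnote, which has no RCM, PK sample, clinical signs or PROs. The fuller list in 9.3.6 follows from a subject's own decision. Even if it is done, SAP 6.4 files it under Early Withdrawal, so it does not supply the Day 28 cure assessment.

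**Step 3: Day 28 clinical cure.** The same failure can be scored in two ways under SAP 6.10.3.4:
- rescued on study and assessed at Day 28: non-responder, in the denominator;
- withdrawn before Day 28: no assessment, not in the denominator.

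With *c* cured out of 6 and *w* failures withdrawn, the reported rate is c/(6 − w). Counting them as non-responders gives c/6. Exact Clopper-Pearson 95% intervals are in brackets.

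| c | w | Reported, c/(6 − w) | As non-responders, c/6 |
|---|---|---|---|
| 3 | 1 | 3/5 = 60% (14.7 to 94.7) | 3/6 = 50% (11.8 to 88.2) |
| 3 | 2 | 3/4 = 75% (19.4 to 99.4) | 3/6 = 50% (11.8 to 88.2) |
| 4 | 1 | 4/5 = 80% (28.4 to 99.5) | 4/6 = 67% (22.3 to 95.7) |
| 4 | 2 | 4/4 = 100% (39.8 to 100) | 4/6 = 67% (22.3 to 95.7) |

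Dropping a non-responder can only raise the rate, or leave it unchanged if nobody is cured.

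**Step 4: primary mite endpoints.** Suppose 1 of 6 subjects is withdrawn with all index mites alive, all other mites die, and each subject has *m* index mites. Carry-forward gives 5m/6m = 83.3%, whereas exclusion would give 100%. The planned rule keeps this failure in the result, although its later status is carried forward rather than observed.

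**Step 5: late safety.** The chance of seeing at least one late AE of true rate *p* among *n* subjects followed is 1 − (1 − p)^n.

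| p | n = 6 | n = 4 |
|---|---|---|
| 10% | 46.9% | 34.4% |
| 20% | 73.8% | 59.0% |
| 30% | 88.2% | 76.0% |

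**The case against.** The strongest defence is that 14.2 only permits withdrawal. It sits beside a retention duty, and rescue under 11.2.3 offers an on-study route for failures from Day 14. That stands. However, the duty is lifted for safety withdrawals, and nothing directs a failure to rescue rather than withdrawal. It is also fair that clinical cure is exploratory, that the intervals above overlap heavily, and that the denominator rule applies to any missed visit. A failure assessed at Day 14 and withdrawn later still appears in the Day 14 cure table, and SAP 6.5 tabulates withdrawal reasons.

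A reader might infer more than the documents support:

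- **That follow-up is lost in precisely the subjects the dose failed or harmed.** The right is discretionary and also covers concurrent illness, administrative and other reasons. Follow-up does not simply stop: 14.4 follows ongoing AEs where possible, and 12.9 follows pregnancies to outcome.
- **That the primary endpoint hides withdrawn failures.** Subjects with live index mites stay in as alive. If the index mites died and new mites appear, SAP 6.10.1.3 scores 100% dead whether or not the subject stays, so withdrawal changes nothing there.
- **That an early AE withdrawal loses nearly all AE data.** On its face, 12.2.2 keeps AE reporting open to at least 28 days after the dose. At most (84 − 28)/84 = 56/84 = 67% of the window for new AEs is at risk. Scheduled laboratory tests end at Day 28 in any case.
- **That the Steering Committee would mistake efficacy failures for poor tolerability.** Section 13 does list "Safety outcomes, such as the frequency, nature and severity of adverse events, and withdrawal rates", but the Committee is unblinded, sees mite mortality and may review line listings. Confusion would be speculation.

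**Conclusion.** The point holds as a gap in follow-up and in one analysis rule. The permission in 14.2 does not fit 12.6 and 14.3. The exit visit does not clearly cover investigator withdrawals, and no text keeps such subjects on the schedule.

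The main exposure is Day 28 clinical cure, where investigator discretion can decide whether a failure counts. In the assumed example of 4 cured and 2 failures, the rate moves from 67% to 100%. That is the extreme case, requiring both failures to be withdrawn before Day 28. One withdrawal gives 80%. The remaining PROs up to Day 28 and the scheduled Week 12 safety data can also be lost. The primary mite endpoints are largely protected.

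This should be corrected because the fix is small and the arms are small. It does not undermine the primary efficacy analysis. How often investigators would use the permission is unknown; the documents give no expected withdrawal rate.

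**What to change.** 1. **Protocol.** Reconcile 14.2 with 12.6 and 14.3, and reconcile 9.3.6 and 14.4 with the Table 1 footnote and 14.5. State that dosed subjects who still consent, and for whom procedures are judged safe, continue the scheduled assessments to Day 28 and Week 12 whatever treatment they then receive. State also that the 9.3.6 exit assessments apply to investigator-initiated withdrawals. Clinical management of AEs, pregnancy and treatment failure stays with the sponsor and investigators. AEs and pregnancy need not be struck out as grounds for withdrawal.
2. **SAP 6.10.3.4.** Add one sentence: a subject whose recorded reason for withdrawal is treatment failure counts as a non-responder at later visits, in line with the rescue rule. This assumes that the CRF reason field identifies treatment failure.

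The cost is one protocol paragraph, submitted to the ethics committee under 16.1.4, and one SAP sentence, settled before the blind is broken for the Day 28 analysis. The visits are already in the schedule. The downside is a possibly lower reported cure rate and some follow-up that is harder to obtain.

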### **14.3 Withdrawal of Subjects from Study Product**

Treatment withdrawal is not relevant in this single dose study.

If a subject is unable to swallow all required tablets and take the full dose of IMP, they should remain on-study and be followed up according to the protocol.

### **14.4 Withdrawal of Subjects from the Study**

Should a subject decide to withdraw from the study, all efforts will be made to complete the study procedures as thoroughly as possible.

If possible, the reason for withdrawal should be determined. The reason for withdrawal should be established by the Investigator through phone contact, a personal visit or by contacting a responsible relative. The reason for withdrawal should be included in a complete final evaluation which should be conducted at the time of the subject withdrawal. If applicable, where possible, subjects should be followed until ongoing AEs have been resolved or abnormal laboratory tests have returned to normal.

### **14.5 Replacement of Withdrawn Subjects**

Any subjects who discontinues in a clinical study of their own volition or by the Investigator are defined as “withdrawals”. Replacement subjects may be enrolled into the study at the request of the Sponsor. They will receive the same treatment allocation as the withdrawn subject by use of a matching replacement subject number pre-assigned for each subject. This is to ensure that blinding is maintained. Further details are provided in the Study Reference Manual.

### **14.6 Premature Termination of the Study**

The study will be completed as planned unless the following criteria are met:

- New information regarding the safety or efficacy of the study drug that indicates a change in the risk/benefit profile of the IMP, such that the risks and benefits of the study are no longer acceptable to study subjects.
- Significant violation of good clinical practice (GCP) that compromises the ability to achieve the primary study objective or compromises subject safety.

Conduct of the study at an investigational site may be terminated if the Investigator or site staff are found in significant violation of GCP, the protocol or other contractual agreements, or are unable to ensure adequate performance of the study.

In the event that the Sponsor elects to terminate the study or an investigational site, an early termination procedure will be provided by the Sponsor, which will be followed by the investigational site(s) during the course of termination.

## 15 STATISTICAL ANALYSIS

### 15.1 Statistical Methods

The study is a randomized, double-blind, proof-of-concept trial designed to describe the association between single moxidectin doses and various parasitological outcomes observed over a 28-day follow-up period. Subjects will continue to be followed for safety to Week 12. Following Screening, eligible consenting subjects will be randomized to one of the 3 initial moxidectin dose groups, 2, 8, or 20 mg. The randomization will be stratified by site and within each site subjects will be randomized using a 1:1:1 allocation ratio. After review of the accumulating data by the Protocol Steering Committee, the randomization scheme may be modified to accommodate the addition or deletion of doses such that the final target sample size of 6 subjects per dose retained/added after the unblinded data review is accommodated. The primary objective of this proof-of-concept study is to identify an optimal dose of moxidectin for further study.

The target sample size,  $n = 6$  per completed dose group, was selected to be practical and an adequate sample size for full characterization of pharmacokinetic profile across the dose ranges studied. Sample size was not based on formal power considerations with respect to statistical hypothesis testing, and as such, the focus of the statistical analysis will be descriptive and exploratory. Nonetheless, statistical models for estimation and hypothesis testing to assess various parasitological assessments with respect to dose may be conducted. It is recognized that the sample size may not adequately support more complex models. When this is the case it will be noted. Given the exploratory nature of the study, no adjustment for multiple comparisons or Protocol Steering Committee data reviews will be made. Given the small sample size per dose group, descriptive analyses per site may be difficult to interpret.

For most analyses, the unit of analysis will be the subject; however, some analyses may be conducted where the unit of analysis may be the individual scabies mite. When this is the case, the unit of analysis will be clearly identified. Analyses using the individual scabies mite as the unit of analysis will address the potential lack of independence between mites belonging to the same subject.

General statistical methods of analysis are described below with more detailed descriptions to be provided in the Statistical Analysis Plan (SAP). The SAP will be finalized prior to breaking the blind for the final analysis. Any changes to the statistical analysis plan made after the blind break will be identified in the clinical study report (CSR).

### 15.2 Hypothesis

Study data will be analyzed in a descriptive manner with the objective of describing an exposure-response association between the moxidectin dose groups and parasitological outcomes and/or observing a single exposure or dose that appears to have the “best” parasitological effect while maintaining an acceptable safety profile.

### 15.3 Sample Size Determination

The sample size chosen for this study, approximately 6 subjects per dose group, was selected to be practical and an adequate sample size for full characterization of pharmacokinetics profile across the dose ranges studied. Sample size was not based on formal power considerations with respect to statistical hypothesis testing.

## 15.4 Analysis Sets

### 15.4.1 Full Analysis Set

The Full Analysis Set (FAS) is defined as all randomized subjects receiving at least one dose of study drug with observed data for the particular analysis undertaken. Subjects in the FAS analysis set will be analyzed according to the dose group to which they were randomized. In general, the FAS will be used for selective analyses such as sensitivity analyses.

### 15.4.2 Per Protocol Analysis Set

The Per Protocol Analysis Set (PPAS) will include all subjects exposed to study drug without any major protocol deviations that could confound the assessment and/or interpretation of the analytic results. The identification of these protocol deviations will be identified by the study team prior to breaking the study blind. Subjects in the PPAS will be analyzed according to the actual treatment received regardless of their randomized dose group. In general, PPAS subjects with missing data for a specific analysis will be excluded from that analysis. It is not anticipated that missing data will be imputed. As this is a proof-of-concept study, the PPAS will be the primary analysis set used to assess parasitological outcomes as well as clinical signs and symptoms endpoints. Replacement subjects will be included in the PPAS if they meet the PPAS requirements.

### 15.4.3 Safety Analysis Set

The Safety Analysis Set (SfAS) will include all subjects exposed to study drug. Subjects will be analyzed according to the actual dose of study drug received regardless of their randomized dose group. Unless otherwise noted, the SfAS will be used for all safety analyses.

